5.1.2 Exclusion Criteria

Subjects are to be excluded from the study if they meet any of the following criteria:

1. History of Richter's transformation or prolymphocytic leukemia
2. Autoimmune hemolytic anemia (AIHA) or idiopathic thrombocytopenic purpura (ITP) that is uncontrolled or requiring $>$ 20 mg once daily (QD) of prednisone (or equivalent) to maintain hemoglobin $>$ 8.0 g/dL or platelets $>$ 10,000 μ L without transfusion support
3. Refractory to ofatumumab (defined as progression or relapse $<$ 12 months of receiving ofatumumab monotherapy or $<$ 24 months of receiving an ofatumumab-containing regimen)
4. Prior allogeneic transplant (prior autologous stem cell transplant $>$ 6 months prior to study entry is permitted)
5. Known central nervous system (CNS) lymphoma or leukemia; subjects with symptoms of CNS disease must have a negative CT scan or negative diagnostic lumbar puncture prior to randomization
6. Prior exposure to a PI3K inhibitor (eg, GS-1101, duvelisib) or a Bruton's tyrosine kinase (BTK) inhibitor
7. Use of any of the following medications or procedures within the specified timeframe:
 - Use of live or live attenuated vaccines within 30 days prior to randomization
 - Chemotherapy, radiation therapy, or ablative therapy within 3 weeks of randomization
 - Tyrosine kinase inhibitor within 7 days of randomization

- Other investigational therapy (not included above) within 3 weeks of randomization
- 8. Ongoing treatment with chronic immunosuppressants (eg, cyclosporine) or systemic steroids > 20 mg prednisone (or equivalent) QD.
- 9. History of tuberculosis treatment within the preceding two years
- 10. Ongoing systemic bacterial, fungal, or viral infections at the time of initiation of study treatment (defined as requiring intravenous [IV] antimicrobial, antifungal or antiviral agents)
 - Subjects on antimicrobial, antifungal or antiviral prophylaxis are not specifically excluded if all other inclusion/exclusion criteria are met and there is no evidence of active infection at randomization
- 11. Human immunodeficiency virus (HIV) infection
- 12. Prior, current or chronic hepatitis B or hepatitis C infection
- 13. History of alcohol abuse or chronic liver disease (other than metastatic disease to the liver)
- 14. Unable to receive prophylactic treatment for pneumocystis or herpes simplex virus (HSV)
- 15. Baseline QTcF > 480 ms (average of triplicate readings) Note: This criterion does not apply to subjects with a right or left bundle branch block (BBB)
- 16. Unstable or severe uncontrolled medical condition (eg, unstable cardiac function, unstable pulmonary condition), or any important medical illness or abnormal laboratory finding that would, in the investigator's judgment, increase the subject's risk while participating in this study
- 17. Concurrent active malignancy other than nonmelanoma skin cancer or carcinoma in situ of the cervix, bladder, or prostate not requiring treatment. Subjects with previous malignancies are eligible provided that they have been disease free for ≥ 2 years
- 18. History of stroke, unstable angina, myocardial infarction, or ventricular arrhythmia requiring medication or mechanical control within the last 6 months
- 19. Administration of medications or foods that are strong inhibitors or inducers of CYP3A within 2 weeks of randomization
- 20. Prior surgery or gastrointestinal dysfunction that may affect drug absorption (eg, gastric bypass surgery, gastrectomy)
- 21. Major surgery or invasive intervention within 4 weeks prior to randomization
- 22. Pregnant or breastfeeding women
- 23. Hypersensitivity to ofatumumab or its excipients

6 STUDY PROCEDURES AND ASSESSMENTS

The Schedules of Assessments are summarized in [Table 1](#), [Table 2](#), [Table 3](#), [Table 4](#), and [Table 5](#). Details related to the assessments are described below.

6.1 INFORMED CONSENT

Subjects potentially eligible for participation must sign an informed consent form (ICF) prior to initiating any study specific procedures. Standard of care assessments that fulfill study eligibility requirements may be performed prior to subject signing the ICF.

6.2 SCREENING PERIOD

6.2.1 Medical History, Physical Examination, and Screening Assessments

The Investigator at the site is responsible for maintaining a record of all subjects screened and those who are enrolled into the study.

During the screening visit, the following assessments will be performed:

- Obtain signed ICF
- Review inclusion/exclusion criteria
 - Prior histologic confirmation of CLL or SLL
- Complete medical history: includes demographics, cancer history and documentation of all previous treatments and treatment results (ie, best response to previous disease specific treatments) prior procedures, current medications, and all medications used within 30 days prior to Screening
- Obtain/confirm documentation of cytogenetics/FISH results with analysis for del(17p). In order to be valid, these previous results must be within 24 months (2 years) of randomization. Additional results for other cytogenetic abnormalities will be collected (if available)
- Full physical examination, which includes vital signs (temperature, blood pressure [sitting for 5 minutes], pulse rate, and respiratory rate), height, and weight
- ECOG* performance status (see [Appendix 4](#))
- Disease-related constitutional symptoms, (fatigue [as measured by ECOG Performance Status], fever [ie, temperature >38°C/100.5°F] without evidence of infection, weight loss, and drenching night sweats without evidence of infection
- Subject-reported health-related QoL* questionnaires (EQ-5D and FACIT-F) will be administered at Screening. If these instruments are not captured at Screening (< 7 days prior to Day 1 Cycle 1), then these assessments must be assessed at Cycle 1 Day 1 predose; English language examples of these instruments are shown in [Appendix 5](#) and [Appendix 6](#)
- 12-lead ECG which should be conducted following an approximate 10-minute rest period in a semi-recumbent or supine position and obtained in triplicate within approximately a 5

minute time period. QTc measurements will use the Fridericia's correction method (QTcF).

- Blood chemistry laboratory parameters* (including liver function tests): sodium, potassium, chloride, bicarbonate (or CO₂), albumin, total protein, creatinine, blood urea nitrogen (BUN) or urea, lipase, amylase, uric acid, calcium, phosphorus, magnesium, glucose, LDH, serum ALT, serum AST, total and direct bilirubin, and alkaline phosphatase.
- Hematology laboratory parameters*: red blood cell (RBC) count, hemoglobin, hematocrit, platelets, white blood cell count with 5-part differential (neutrophils, lymphocytes, monocytes, eosinophils, basophils) such that an absolute neutrophil count (ANC) and an ALC can be derived if it is not already provided as part of the laboratory analysis, and coombs testing (direct and indirect). Documentation of hematology labs within 7 days prior to randomization is required to confirm presence or absence of Grade 4 cytopenia for stratification at randomization.
- Coagulation laboratory parameters* including prothrombin time (PT), and activated partial thromboplastin time (aPTT). For subjects receiving anticoagulation therapy affecting the PT, an International normalized ratio (INR) must be obtained.
- Anti-hepatitis C antibody (HCV Ab), hepatitis B surface antigen (HBsAg) and hepatitis B core antibody (HBcAb).
- Laboratory studies to assess the status of prior or current Cytomegalovirus (CMV) and Epstein-Barr virus (EBV) infection. These may include any or all of the following: CMV Ab (via a serology) and antigen [viral load detection via polymerase chain reaction (PCR)] or immunohistochemistry (pp65 CMV) and Epstein-Barr virus serology.
- Serum pregnancy test for WCBP (must be performed within 7 days of randomization)
- HIV test for all subjects without documentation of a prior negative HIV test
- Baseline disease assessments, which include:
 - CT scans of chest, abdomen and pelvis are required for all subjects. Other scans may be performed (eg, head/neck CT) if clinically indicated or if the area is a site of known disease. Copies of all imaging/radiology films will be sent to a central laboratory for independent review.
 - **Note:** Magnetic resonance imaging (MRI) may be substituted if clinically indicated, but the modality chosen to evaluate each individual subject should be the same throughout the duration of the study.
 - Bone marrow aspirate and/or bone marrow biopsy (unless clinically contraindicated).

** ECOG, QoL, hematology, liver function tests, blood chemistry, or coagulation evaluations may be performed within 7 days prior to study treatment (predose Cycle 1 Day 1). If these Screening evaluations are performed within 7 days of Cycle 1 Day 1, these Screening results can be used in place of the Cycle 1 Day 1 assessments.*

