- c. Additional (unscheduled) assessments should be done as clinically indicated. Blood samples should be drawn and results reviewed within 72 hours of the designated clinic visit.
- d. Screening evaluations performed within 7 days of Cycle 1 Day 1 can be used and assessments do not need to be repeated at Cycle 1 Day 1 (predose)
- e. Drawn only on Day 1 of Cycles 3, 5, 7, 11, 15, 19, and ETT. Blood for immunophenotyping, serum for biomarkers, and blood for biomarkers do not need to be collected beyond the ETT visit or treatment discontinuation.
- f. May be either urine or serum, and performed every odd cycle while on treatment.
- g. To be sent to the central laboratory.
- h. Sample may be drawn at screening or Cycle 1 Day 1 (predose). Collection at Cycle 1 Day 1 is preferred. If drawn at screening, a sample is not needed at Cycle 1 Day 1.
- i. This sample will be analyzed centrally and is separate from the documentation of prior del(17p) analysis required for eligibility and stratification.
- j. Additional blood for immunophenotyping/biomarker serum samples may be requested from any subject receiving duvelisib at qualified sites (when feasible) at the time of a drug interruption/hold due to an AE, or for any usual safety event or efficacy event.
- k. Samples on Cycle 1 Day 1 should be drawn predose.
- l. Pharmacogenomics sample (buccal swab) is optional.
- m. QoL assessments to be captured at on Day 1 of Cycles 3, 5, 7, 11, 15, and 19 until disease progression, subject withdrawal, or initiation of additional anticancer therapy, and when possible, at the ETT (if >1 month from last administered questionnaire).
- n. Requests for archival tissue (pretreatment sample) should be initiated at Cycle 1 Day 1. In the event a request is placed but no archival tissue can be located, this sample type is not required.
- o. Subjects who discontinue treatment from duvelisib prior to Cycle 19 Day 1 for reasons other than PD, will maintain the clinical visit schedule through Cycle 19 Day 1 until disease progression, subject withdrawal, or initiation of additional anticancer therapy.
- p. Subjects who, in the judgment of the investigator, may derive benefit from continued treatment, may receive additional cycles of duvelisib beyond Cycle 19 Day 1 until disease progression or unacceptable toxicity. .

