4 STUDY DESIGN

Study IPI-145-07 is a two-arm, randomized (1:1 ratio), open label, phase 3, superiority trial designed to evaluate the efficacy and safety of duvelisib compared to ofatumumab. Subjects will be stratified by:

1. High-risk cytogenetics (presence vs absence of del[17p])
2. Refractory/early relapse to purine analog based therapy (defined as progression < 12 months after fludarabine/pentostatin: yes vs no)
3. Grade 4 cytopenia(s) (presence vs absence of neutropenia or thrombocytopenia at baseline)

Eligible subjects will be randomized in a 1:1 ratio to one of two treatment arms:

- Arm 1: Duvelisib, 25 mg BID
- Arm 2: Ofatumumab

First dose is to occur within 7 days of randomization after all screening assessments have been completed.

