6.3.1.3 ECOG Performance Status

For Cycle 1 Day 1 (predose), the ECOG performance evaluation may be performed within 7 days prior to study treatment (Cycle 1, Day 1). If the ECOG performance evaluation is performed within 7 days of Cycle 1 Day 1, this Screening result can be used in place of the Cycle 1 Day 1 ECOG performance.

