7.6 ASSIGNMENT TO TREATMENT

Once a subject has met all entry criteria, the IRT will be used to generate a distinct subject identifier. Eligible subjects will be randomized within 7 days prior to receipt of first dose of study drug. If a subject discontinues from the study, the subject identifier will not be reused and the subject will not be allowed to re-enter the study.

Eligible subjects will be randomized via IRT in a 1:1 ratio to one of two treatment arms:

- Arm 1: Duvelisib 25 mg BID

- Arm 2: Ofatumumab

In order to ensure subject balance between treatment groups, study subjects will be stratified by the following:

- High risk cytogenetics (presence vs absence of del[17p])
- Refractory/early relapse to purine analog based treatment (progression <12 months after fludarabine/pentostatin: yes vs no)
- Grade 4 cytopenia(s) (presence vs absence of neutropenia or thrombocytopenia at baseline)

Randomization is to occur within 7 days of first dose after all screening assessments have been completed.

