## 6.8 Baseline Values

Unless otherwise specified, the baseline value is defined as the value collected at the time closest to, and prior to, the start of study drug administration. Values collected at unscheduled visits prior to the start of the study drug administration will be included in the calculation of baseline values.

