### 7.2.3 **Analyses of Exploratory Efficacy Endpoints**

#### 7.2.3.1 *Improvement in Disease-Related Symptoms*

Disease-related symptoms of fever, weight loss, and drenching night sweats will be assessed as present or absent at each timepoint. Improvement in each of the three disease-related symptoms from baseline will be analyzed separately. The summary will display by treatment arm the proportion of subjects with an improvement while on treatment. Descriptive analysis of improvement in these disease-related symptoms will also be presented over the course of the study (eg, for each scheduled assessment) by treatment arm.

The disease-related symptom of fatigue will be measured by the ECOG performance status. Summary statistics will be provided by treatment arm for the ECOG score and the change from baseline at each timepoint.

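### In this open-label trial the EQ-5D, FACIT-F and ECOG baseline can be taken after randomization, and SAP 6.8 then uses that value in place of an earlier one

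*Protocol*

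**What the plan says.** **Timing of randomization.** Protocol 4 states "First dose is to occur within 7 days of randomization after all screening assessments have been completed", and Protocol 7.6 states the same interval from the other side: "Eligible subjects will be randomized within 7 days prior to receipt of first dose of study drug". Protocol 10.8 describes the study as open-label, with individual assignments known to investigators, site staff and the sponsor. Subjects will know theirs too, since one arm takes capsules and the other receives infusions.

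**Timing of the measures.** EQ-5D and FACIT-F are on the Screening checklist (Table 1), but Protocol 6.2.1 adds "If these instruments are not captured at Screening (< 7 days prior to Day 1 Cycle 1), then these assessments must be assessed"; the time it names for this is Cycle 1 Day 1, before dosing. Note d of Table 2 puts the waiver as "Screening evaluations performed within 7 days of Cycle 1 Day 1 can be used and assessments do not need to be repeated", and Table 4 carries an equivalent note. For ECOG, Protocol 6.3.1.3 says of an evaluation made within 7 days of Cycle 1 Day 1 that "this Screening result can be used in place of the Cycle 1 Day 1 ECOG performance".

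**Definition of baseline.** SAP V4.0 section 6.8: "the baseline value is defined as the value collected at the time closest to, and prior to, the start of study drug administration". That definition gives way to exceptions stated elsewhere, but SAP 7.4 (quality of life) and 7.2.3.1 (symptoms) state none.

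**Use of baseline.** SAP 7.4.1 and 7.4.2 summarize change from baseline for the EQ-5D VAS and the FACIT-F scores. SAP 7.2.3.1 says "The disease-related symptom of fatigue will be measured by the ECOG performance status" and summarizes change in ECOG by arm. SAP 6.5 splits treatment-emergent adverse events by baseline ECOG (0 or 1 vs 2).

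**The concern.** A baseline should be fixed before the assignment can influence it. Two of these measures are self-reported and the third is rated by site staff who know the arm. A value taken after assignment may already contain a reaction to it, such as relief or disappointment in the subject or expectation in the rater. As the reference for change from baseline, that value carries the reaction with opposite sign into each of the subject's change scores.

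Protocol 6.3.5 itself asks for every effort to keep the questionnaire assessment unbiased. FACIT-F also asks about the past 7 days (Appendix 6). For a subject dosed 7 days after randomization, a Cycle 1 Day 1 FACIT-F therefore recalls essentially only time after randomization. Elsewhere in Protocol 6.2.1 the hematology used for stratification and the pregnancy test are timed against randomization, so the same could have been done here.

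**Working it through.** No stated sample size, power or alpha depends on this point, so there is no plan figure to reproduce. The check is to follow the timing rules through to the value that SAP 6.8 selects.

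**Step 1: which value becomes baseline**

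- Screening value inside the 7-day window, before randomization, not repeated: it is the last predose value, so baseline precedes randomization. No problem.
- Screening value inside the window, but Cycle 1 Day 1 also done (the waiver is optional): the Cycle 1 Day 1 value is closer to first dose and is selected.
- Screening value older than the window: Cycle 1 Day 1 is called for and its value is selected. The earlier value exists but is not used.
- No Screening questionnaire: Cycle 1 Day 1 is the only value.

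In the last three cases baseline follows randomization, unless randomization and dosing fall on the same day and the measure is taken before the assignment. The protocol does not require that order. The third case is not exotic: Table 1 lets Screening run to 30 days before dosing, and days 8 to 30 (23 of the 30) lie outside a 7-day window.

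**Step 2: how often a pre-randomization value can waive the Cycle 1 Day 1 repeat**

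Let g be the days from randomization to first dose (0 to 7) and d the days from the Screening assessment to first dose. The waiver needs d < 7 (text of Protocol 6.2.1 on the questionnaires) or d ≤ 7 (the footnote to 6.2.1, Tables 2 and 4, and 6.3.1.3). The assessment precedes randomization if d > g, or if d ≥ g when a measure taken on the randomization day comes before the assignment. The number of qualifying days is 6−g (not below 0) or 7−g for d > g, and 7−g or 8−g for d ≥ g.

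| g | d<7, d>g | d≤7, d>g | d<7, d≥g | d≤7, d≥g |
|---|---|---|---|---|
| 0 | 6 | 7 | 7 | 8 |
| 1 | 5 | 6 | 6 | 7 |
| 2 | 4 | 5 | 5 | 6 |
| 3 | 3 | 4 | 4 | 5 |
| 4 | 2 | 3 | 3 | 4 |
| 5 | 1 | 2 | 2 | 3 |
| 6 | 0 | 1 | 1 | 2 |
| 7 | 0 | 0 | 0 | 1 |

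The room for a qualifying pre-randomization value shrinks day by day as the gap grows. At g = 7 it is none or one day, depending on wording and convention. Averaged over eight equally likely gaps it is 21/8 = 2.6 to 36/8 = 4.5 days, but equal likelihood is an assumption: the documents give no distribution of g.

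**Step 3: effect on the summary**

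If a share p of an arm has a post-assignment baseline and the assignment shifts those values by δ on average, that arm's mean change moves by −p × δ. The documents give neither p nor δ. As an illustration only, an assumed δ of 1 to 3 points on the 0 to 52 Fatigue subscale with p anywhere from 0 to 1 gives a movement of 0 to 3 points.

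**The case against.** **The 7-day rule is not a test of validity.** It decides only when the Cycle 1 Day 1 repeat may be skipped; an older Screening value is not declared invalid. A reader might infer from the table that a subject dosed 7 days after randomization can have no valid pre-randomization baseline. The documents do not support that. Such a subject may well have one, and the difficulty is that SAP 6.8 passes over it. This objection stands.

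**Pre-randomization values are already expected.** The questionnaires are due at Screening, and Protocol 7.6 places randomization after the screening assessments. ECOG 0 to 2 is an inclusion criterion, so every properly enrolled subject has a pre-randomization ECOG. This also stands, and it makes the SAP change easy. It does not remove the point, because the SAP still prefers the later value.

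**A post-assignment baseline may cancel bias.** All follow-up is open-label. Let the shift from knowing the arm be δ0 at Cycle 1 Day 1 and δt at visit t, with drug effect τ. Change from a pre-randomization baseline is τ + δt; change from a post-assignment baseline is τ + δt − δ0. If the reaction is stable (δt = δ0), the later baseline removes it. If it fades (δt = 0), the later baseline adds an error of −δ0. The documents do not show which applies, so the direction of bias is open and both versions deserve a summary. The case for the earlier baseline is that assignment cannot have affected it.

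**The stakes are low.** The endpoints are exploratory and the planned analyses are descriptive, with no between-arm test. FACIT-F actual values and EQ-5D dimension proportions at post-baseline visits do not use baseline at all. This stands and limits the point.

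**Conclusion.** The point holds in a limited form. For subjects whose Cycle 1 Day 1 assessment is done, for example because Screening was more than 7 days before dosing, a value taken up to 7 days after open-label assignment becomes the reference for change from baseline, displacing any earlier value. It touches the descriptive change summaries of FACIT-F, EQ-5D VAS and ECOG-measured fatigue, and the adverse-event subgroup by baseline ECOG. It does not touch PFS, ORR, OS, alpha, power or sample size.

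Two stronger readings should be resisted. One is that baselines in this trial are generally post-randomization: the waiver leaves an unknown share of subjects with a pre-randomization baseline. The other is that a bias of known size or direction follows: any figure in points is assumed, and the objection shows that the sign can be argued either way. The conclusion rests on reading SAP 6.8 as written, with no exception elsewhere in the SAP, and on subjects learning their arm at or soon after randomization. The latter follows from the open-label design but is not stated for subjects. This is a worthwhile, low-cost improvement and no threat to the trial's main conclusions.

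**What to change.** **Protocol 6.2.1, 6.3.1.3 and Tables 1, 2 and 4.** Have EQ-5D, FACIT-F and ECOG completed before the IRT randomization call. Keep Cycle 1 Day 1 predose only as a fallback, flagged in the data, when no pre-randomization value exists. Removing the fallback altogether would leave a subject with a missed Screening questionnaire without any change score. Use one wording for the 7-day window, since 6.2.1 and the tables differ by a day.

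**SAP 6.8.** For these three measures, define baseline as the last value on or before randomization and before the assignment is known, with the last predose value used only if there is none. Report the number of fallback baselines by arm, and add a sensitivity summary of change using the last predose value for everyone. The SAP change also serves subjects already enrolled, wherever a Screening value was recorded. It gives a defined baseline to subjects randomized but never dosed as well: SAP 7.4 includes them in the ITT quality-of-life analysis, but a baseline tied to first dose leaves them without an anchor.

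**Cost.** Wording in the schedule, a short addition to SAP 6.8 and one extra set of summaries; no added visit. The drawback is a baseline further from first dose, up to the 30-day screening window for subjects already enrolled, and a few subjects whose baseline is defined differently because they needed the fallback.
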